#### 54 **Group 2: Health-IT only group:**

Training at the time of discharge: The Patient Buddy app with preloaded caregiver and patient interfaces will be shown to the subjects and caregivers with detailed instructions including: User Guide of Patient Buddy, Quick Reference Sheets for Case Coordinator to give the Patient and Caregiver with screenshots and tips and tricks for maneuvering around the modules, Powerpoint presentation that goes through the workflows for patients and caregivers, and one on one training for the Case Coordinator given by the CITI Representative. In addition, administration of five orientation questions (what is the date, what is the time, what is the year, who am I and where are you?) and EncephalApp Stroop will be taught to the caregiver. The call-in numbers for the nurse coordinator, GI physician on call and the contact information for the

1 principal investigator will also be programmed into the app. A detailed training session will be performed over the next hour by the coordinator  
 2 and the PI to both the patient and the caregiver. This training will be tailored to the specific issues faced by the patient while they were  
 3 hospitalized. The individualized login and passwords for each patient and their caregiver will be established and given to them. A copy will be  
 4 kept with the nurse coordinator in case the subjects forget their codes. These will be reset upon return of the devices at the end of the study.  
 5 The connectivity and messaging system in-built into the Patient Buddy App will then be checked and the control center of the CITI  
 6 communications notified of this enrollment. This will also be checked by sending messages by the patient and caregiver through the App to  
 7 the coordinator and the PI (Figure 3 demonstrates the data flow). In the health-IT only group, there will be daily contacts between patients,  
 8 caregivers and the clinical teams via the App. The only visit scheduled for the study will be at day 30 when the study will be completed.  
 9 However, if there are issues that come up during the intervening period detected via the App, the clinical team will reach out and determine  
 10 with the patients and caregivers if an ad hoc intervening visit is required. The team will not meet with patients or caregivers if they are scheduled  
 11 to be seen as standard of care in their clinics in between the 30 days unless specifically required by the symptoms or if the patient requires  
 12 readmission. If the patient requires readmission before day 30, their participation will end at that time.

13 **Group 3: Health-IT+Scheduled Follow-up Group:**

14 This group will undergo the training at discharge similar to what was performed in group 2 but we will also intersperse the 30 day follow up with  
 15 one visit and 2 scheduled phone calls as below. Visit Scheduled: Patients and caregivers will be formally called at day 7 and 21 post discharge  
 16 by the study team to inquire about issues that were not communicated via PatientBuddy. We will also perform a study visit at day 15 and day  
 17 30 with both patients and caregivers to define any new changes in the patient's condition, elicit feedback throughout the process and at the day  
 18 visit, returning the devices and resetting them. No additional charges will be generated from the study during these visits.

19 The week 2 visit will include vital signs as well as the discussion of any issues with the buddy app, patient medication update, and any new  
 20 medical issues. The subject will also be given the EncephalApp stroop and orientation test for the week like in group 2. Study staff may also  
 21 observe the caregiver and subject perform their daily app entries. (subject may document medications taken, abdominal girth measurement,  
 22 and daily weight. The caregiver may document medications, daily weight, abdominal girth, orientation questions and stroop test) The study  
 23 staff will offer guidance as needed to complete these tasks. If the patient has a >10lb weight gain from baseline, a >5 inch girth increase, and/  
 24 or is febrile, the study team will notify the hepatologist on service and the PI for direction. No blood will be collected for the study and/or tests  
 25 run for study purposes at any time. However, if the subject is febrile, has overt encephalopathy, is bleeding, and/or is more decompensated,  
 26 the study team will alert the medical team and coordinate care as needed. Any care performed as a result of the findings from this visit will be  
 27 conducted per standard of care by the medical team."

28 FOR GROUPS 2 AND 3: If the subject is re-admitted, they meet the endpoint and their participation will  
 29 end. We will contact the caregiver and coordinate a return of the smartphones and end of study elements. We will also  
 30 request a discharge summary from the outside hospital if they were hospitalized outside of McGuire VAMC. If the patient  
 31 is in-house, we will coordinate the end of study while in the hospital if appropriate. The phones distributed to the  
 32 participants in groups 2 and 3 are not capable of making phone calls and have a restricted data plan under CITI. Only  
 33 data entered in the Patient Buddy App will be transmitted directly to the HIPAA-compliant CITI server. At the end of the  
 34 study (at day 30 or readmission within 30 days), the phones will be turned in and remotely wiped of any data. Therefore,  
 35 any other data generated (browsing, photographs etc) performed by the patient/caregiver on their phones will be wiped  
 36 without transmitting over to any other entity. Therefore, there are no privacy or confidentiality risks pertaining to this.

37 Patient Buddy App Use (for groups 2 and 3): The Patient Buddy App will be loaded onto the phones given to the patients and caregivers by the  
 38 study team with the following data and the instructions to get in touch with the team (Table 3)

39 **Contact through Patient Buddy**  
 40 - Daily contacts pertaining to adherence, cognition and measurements as needed (details below)

41 **Unscheduled contacts:**

42 - If nothing is entered in the Patient Buddy for >24 hours by either patient or caregiver  
 43 - Depending on results of scheduled telephone calls  
 44 - Admissions to McGuire VA medical center or after discharge from other hospitals if admitted  
 45 - Telephone calls generated from patients/caregivers to the study team

46 "The study team will reach out to the patient with an open statement such as :"hello \_\_\_\_\_ we noticed you have  
 47 not recorded anything today, is everything ok...any questions? ' The app will be checked by the study team every day. Since the subjects have  
 48 multiple medical problems and their questions are not uniform, the study team will not have a standardized set of responses; they will utilize  
 49 their medical training to address questions appropriately and in the event of progressive decompensation, will alert the medical team and PI and  
 50 coordinate urgent care. Any care performed as a result of the findings from these communications be conducted per standard of care by the  
 51 medical team." Subjects will also be given the number (as is standard of care) for the GI-physician on call and will also be able to call emergency  
 52 services if they are not able to wait to use Patient Buddy. On the day of discharge, the study coordinator, patient, caregiver and the case  
 53 coordinator will meet for the training and evaluation of the Patient Buddy App as well to check the connectivity.

54 The following data will be collected and reiterated to the patient and the caregiver (Table 3).

55 **Table 3: Patient/Caregiver Logs into the buddy at home daily and to contact study team**

56 Area of interest	57 Specific entry in Patient Buddy	58 To contact study team, GI physician on call or emergency services (marked*)
59 Medication adherence on each medicine on discharge	60 Enter each medicine administration time, date and dose	61 Questions regarding medications, missing or increasing dose
62 New medications and supplements	63 Enter new medicine and dose	64 Call when a new medicine/ supplement is initiated

[figure not shown]
1	Vitals (to be taken at same time every day)	Daily weight	≥3 lb increase in 24 hours
2		Daily Temperature	> 100.4 F or < 96.8 F
3	Cognition (assessed every week or when caregiver feels patient is not acting normally)	Orientation questions (5 questions time/place/person)	Any question abnormal, coma*, confusion, or difficulty waking patient up*
4		EncephalApp Stroop Score	>25 seconds over discharge score(15)
5	Emergency/urgent/other symptoms	Daily bowel movements	<3 or >6 bm/s day (if on lactulose) and any change in those without lactulose
6		GI bleeding (detailed symptoms noted)	Black stools, red blood in stools or vomiting blood*
7		Infections (detailed symptoms noted)	Fever, shortness of breath, burning in urine, abdominal pain, nausea or vomiting
8			
9			
10			
11			

12 The data collected from each patient's medical chart to meet enrollment criteria for this study at discharge will be the  
 13 discharge summary, contact information, and all elements to verify inclusion/exclusion criteria (no  
 14 substance abuse, >21 years of age, non-elective hospitalization, will be discharged home, no dialysis) Also, if the patient is  
 15 re-admitted, discharge summary will again be collected.

16 Training and counseling at the time of discharge: The Patient Buddy app with preloaded caregiver and patient interfaces will be shown to the  
 17 subjects and caregivers with detailed instructions. The call-in numbers for the nurse coordinator, GI physician on call and the contact information  
 18 for the principal investigator will also be programmed in to the app. A detailed training session will be performed over the next hour by the  
 19 coordinator and the PI to both the patient and the caregiver. This training will be tailored to the specific issues faced by the patient while they  
 20 were hospitalized. The individualized login and passwords for each patient and their caregiver will be established and given to them. A copy  
 21 will be kept with the nurse coordinator in case the subjects forget their codes. These will be reset upon return of the phones at the end of the  
 22 study. The connectivity and messaging system in-built into the Patient Buddy App will then be checked and the control center of the CITI  
 23 communications notified of this enrollment. This will also be checked by sending messages by the patient/caregiver through the App to the  
 24 coordinator and the PI.

25 The Patient Buddy App will be loaded onto the Phones given to the patients and caregivers by the study team with the following data and the  
 26 instructions to get in touch with the team.

27 The Patient and Caregiver Patient Buddy Initial Screens after Login are shown in Figure 4

The caregivers and patients will independently log in and provide updates as needed on action items that lead from each icon. All important items in the discharge counseling are in the home screen for patients and caregivers.

#### Role of caregivers:

Caregivers will be given instructions on cognitive testing and EncephalApp Stroop testing and the use of the weighing machine and tape measure for measuring weight and abdominal girth respectively. Caregivers will be instructed to give the orientation questions and EncephalApp Stroop to the patient if they appear not behave normally or once per week after discharge.

EncephalApp is a validated test of cognitive functioning in cirrhosis, which consists of an easier Off state and a harder On state. The respondents have to correctly identify the color red, green or blue in presented "#" symbols during the Off state while in the On state they still have to pick the correct color from words presented in a discordant color. E.g. the word "GREEN" will be presented in a blue color and the correct answer is blue not green. There are 2 training runs for each state and the patient has to complete 5 complete runs in both states. The total time to complete 5 runs in the Off and 5 runs in the On state is the "OffTime+OnTime" which is noted in the Patient Buddy App once this is presented to the patient every week by the caregiver.

While we aim to prevent all readmissions, the focus is to disseminate information through Patient Buddy on three specific preventable areas that are responsible for a majority of readmissions:

1 (A) Hepatic Encephalopathy, (B) Ascites and fluid/electrolyte management (C) Infections

2 The following will be performed jointly between caregivers, patients and study team to prevent readmission. Prevention

3 of recurrent episodes of hepatic encephalopathy:

4 - Ensure patients are started on medications appropriately on discharge.

5 - Involve the caregiver at all levels of care, including cognitive/orientation testing as needed

6 - Ensure patients are taking the specific dose of medications (a) Reduce lactulose dose if patient is dehydrated (b) increase

7 lactulose dose if patient is not clear mentally.

8 - Simple orientation questions and EncephalApp Stroop to gauge changes in cognition.

9 - Early clinic appointments to treat HE and prevent hospitalization or worsening of disease.

10 Management of ascites, fluid and electrolyte issues:

11 - Reiterate the dosage schedule of diuretics at discharge and daily entry of diuretic doses, weight and abdominal girth (example in

12 **figure 6)**

13 - 2gm Na diet if indicated and daily charting of the adherence

14 - Stop diuretics and contact nurse coordinator in case the patient is dizzy or lightheaded

15 Prevention of recurrent infections:

16 - Adherence on antibiotics to complete therapy as needed and/or adherence on SBP prophylaxis

17 - Education of caregivers that HE could indicate infection.

18 - Call or alert team immediately if patient has fever, chills, nausea or abdominal pain

20  
21 **Figure 6: Nurse Manager Screens showing medication adherence**

36  
37 The nurse coordinator receives data continuously throughout the day, monitors all values from the patients and caregivers on their iPad. They  
38 will alert the patient/caregivers with alarm issues and contact the PI/ physician-on-call if urgent action is required. On the weekends and after  
39 hours, there will be coverage of the iPad with [name] and [name]. As mentioned above, subjects and caregivers will again be  
40 told about the need to communicate urgent issues with the GI fellow on call rather than waiting for a response in the App.

41 The App gives caregivers and patients

42 A. An opportunity to directly communicate with the study team

43 B. Guidance as to when to call emergency services

44  
45 No other medical information or advice is in-built in the App, but it largely forms a conduit between the study team and patient/caregivers.

46  
47 The nurse study coordinators will regularly provide feedback to the app developers regarding the app. This feedback will be informal and will  
48 occur on a rolling basis. The nurse study coordinators will not be surveyed or interviewed formally. Unlike with the formalized patient feedback,  
49 we do not intend to generalize any findings from the nurses' feedback, and will solely use the information they provide for quality improvement  
50 of the app."

51  
52 30 DAY VISIT FOR ALL GROUPS: All patients discharged from the hospital are scheduled for a 30 day follow-up at minimum as a standard

53 of care visit. Some patients will be scheduled for a 2 week follow-up post discharge as standard of care, depending on the reason for admission.

54 The medical team will collect labs, perform a physical exam, and provide routine care tailored to the individual patient and his/her medical  
55 issues on the day 30 visit. These procedures are all standard of care and are not done solely for research purposes. The study team will also  
56 meet with the patient and his/her caregiver at this day 30 visit and will not generate any costs for the pt. We will collect the smartphones and  
57 have the patient and caregiver complete a survey regarding their experience with the app. The pt and caregiver will be together. The questions  
58 to be asked are uploaded to this submission."

59 Decision regarding avoidable readmissions: This will be made by analyzing the discharge summary of the hospitalized patients and will be  
60 classified into avoidable or unavoidable by the committee with three hepatologists (1 each from the 3 sites). The decision regarding avoidability  
is based on the question whether could a clinic visit or earlier communication/education with patient and caregiver prevented this admission.

1 There is no specific hard and fast rule about which admissions are classified as one or the other, which is why a committee is necessary. On  
2 the whole, admissions for elective paracentesis, thoracentesis, early stages of hepatic encephalopathy etc are usually avoidable but those  
3 related to infections, severe hepatic encephalopathy, variceal bleeding etc are usually not considered avoidable. However, since each case is  
4 unique, all discharge summaries of patients admitted within 30 days will be sent to the committee to review and vote. The committee will not be  
told about the assignment of the patients.

5 SAEs: we do not anticipate SAEs i.e. re-admissions to be related to the App itself because that is what is the focus of the study. Therefore,  
6 SAEs simply associated with admissions will not be reported to the IRB. We do not expect other SAEs directly related to the App to appear in  
7 this study.

8  
9  
10  
11  
12  
13  
14 **Active Data Collection**

15  
16. \* **Describe the technology chosen for collecting the data and transmitting data securely over the internet. Give the rationale  
for selecting this technology:**

17 For groups 2 and 3, we will use the Patient buddy app. This has been described in great detail in the uploaded grant but the details are below.  
18 **Patient Privacy and Security:** The App is HIPAA compliant with federal regulations regarding Privacy and Security. Patient Buddy is  
19 considered a Business Associate under the terms of the final HIPAA Omnibus rule. The data management of this study will operate using a  
20 secure hosted environment with a HIPAA compliant server and data storage network. Given the sensitivity and need for security in managing  
21 and handling personal health information, Patient Buddy has developed its application such that no data are stored on either any of the  
22 distributed devices. Only after verification and authentication of login credentials is established with the server, is any data pushed out to the  
23 appropriate devices. All data are transmitted to the server where they are controlled behind the network firewall.

24  
25 **Patient Buddy Design to Protect PHI:** The Patient Buddy App will be hosted at a secure data center using a HIPAA compliant server. The  
26 data center provides several key security features that contribute to the safeguarding of PHI. These data safety and security features include  
27 physical security of the data center and infrastructure; perimeter security of IP reputation; network security for intrusion detection, firewall and  
28 vulnerability; server security for OS, anti-virus and log management; along with procedures and protocols for data backups, security audits,  
29 access control, change controls, and the maintenance of policies and procedures. From an application and program management standpoint,  
30 Patient Buddy offers further security safeguards to protect PHI to include secure data deletion upon termination of services; administrative  
31 security that provides for secure access and two-factor authentication; program access control; security policies and procedures, incidence  
32 response protocols, and risk assessments monitored and updated by our privacy and security officer, as well as data management and  
33 application management processes. All Integration of exports from the EncephalApp Stroop test will be handled with the same security and  
34 privacy concerns. At no time will any PHI be disclosed and all data will be filtered through the HIPAA compliant servers. Data Integration:  
35 Regarding the architecture, Patient Buddy's server application is responsible for the data interchange between the database and the mobile  
36 apps. This can also serve as the integration point with EHR's and third party vendors. The Database uses Microsoft SQL Standard Enterprise  
37 version and it is hosted on virtual machines to reduce deployment time. CITI also uses caged physical servers deployed in geo redundant  
38 locations.

39  
40. \* **Describe how data will be linked or unlinked to identifiers including email addresses, names, and/or IP address. No  
identifiers are in the App or smartphones or iPads**

41  
42. \* **Is there an alternative method for completion of the data collection other than the internet:**

43. **No**

44. **If yes, describe the alternative(s):**

45 The Health IT component is the entire focus of the study; inability or not wanting to use Apps are an exclusion

46. \* **Describe how individuals will be able to skip or not answer particular questions. If any questions are mandatory, provide  
justification:**

47 There are key questions related to

48 a. Medication adherence

49 b. New medications

50 c. Vitals

51 d. Cognitive testing

52

53 Are all essential and will be queried if not entered. These are important because these are the leading causes of avoidable readmissions and  
54 are therefore mandatory.

55

56 **Data Confidentiality and Storage**

57

58 Confidentiality refers to the way private, identifiable information about a participant or defined community is maintained and shared.

59

60. \* **Specify where this study's paper and electronic research data and/or physical specimens will be stored and how they will be**

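### Readmissions are presumed unrelated to the app and are not reported to the IRB, yet the programme involves dose changes and no described review asks whether one contributed to a readmission.

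*Combined protocol and SAP*

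**What the plan says.** **Dose actions.** The Role of caregivers section lists steps shared between caregivers, patients and study team. For lactulose these are "a) Reduce lactulose dose if patient is dehydrated (b) increase" "lactulose dose if patient is not clear mentally". The ascites steps include stopping diuretics and contacting the nurse coordinator if the patient is dizzy or lightheaded. Under the provisions for medical intervention in the event of adverse events, the coordinator may pass on the medical team's instructions and documents them.

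**Safety reporting.** The SAEs paragraph reads "we do not anticipate SAEs i.e. re-admissions to be related to the App itself because that is what is the focus of the study", and concludes that "SAEs simply associated with admissions will not be reported to the IRB". The risks section lists no physical risk from using the app.

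**Review of readmissions.** On the avoidability decision: "This will be made by analyzing the discharge summary of the hospitalized patients and will be" classified by three hepatologists who are not told the assignment. The decision "is based on the question whether could a clinic visit or earlier communication/education with patient and caregiver prevented this admission". Admissions "related to infections, severe hepatic encephalopathy, variceal bleeding etc are usually not considered avoidable". The quarterly call (Non-VA Site Details) asks whether readmissions could have been prevented. Specific Aim 1 promises a detailed readmission analysis and names potential preventability.

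**End of participation.** For groups 2 and 3: "If the subject is re-admitted, they meet the endpoint and their participation will" end.

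**The concern.** The presumption concerns the app as a piece of software. What is tested is a programme in which lactulose may be raised or lowered and diuretics stopped, sometimes on relayed advice. Too much lactulose could end in an admission for dehydration, and too little in one for encephalopathy. Such an admission is an SAE of the kind the protocol does not report, and it is also the trial's endpoint, so it is handled wholly as an outcome.

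Preventability and causation are different questions. The first asks what the programme might have stopped, the second what it might have brought about. If only the first is asked, the trial could end without being able to say whether the intervention's own dosing advice did harm. Anyone considering adoption of the programme would want that answer.

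**Working it through.** **1. Does any described step ask about contribution?**

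| Step | Source named | Question named | Asks whether a programme dose change contributed? |
|---|---|---|---|
| Blinded committee | Discharge summary | Could a visit, earlier communication or education have prevented it? | No |
| Quarterly call | De-identified data | Could it have been prevented? | No |
| Aim 1 analysis | Not specified | Detailed analysis, including preventability | Not stated |
| SAEs paragraph | None | None; unrelatedness is presumed | No |

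The quarterly call and the Aim 1 analysis are worded openly enough for someone to raise the point, but neither sets it as a question. The committee is poorly placed to do so. The app dose log is not described as going to it, and sending the log would reveal that the patient was in a health-IT group.

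**2. Do the records exist?** Largely yes.
- Table 3 has each medicine entered with time, date and dose, and app entries go to the server, so wiping the phone does not remove them.
- Instructions relayed by the coordinator are documented.
- The discharge summary is collected again at readmission.
- One limit: the medical team may call the dyad directly, and the protocol does not say where that advice is recorded. The dose log should still show a change if the entries were made.

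**3. How many readmissions would need checking?**

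Inputs: 232 patients (Protocol Amendment 2); 33% readmitted at 30 days, avoidable share 20% falling to 9% (sample size justification).

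The number already allocated 1:1:1 before the change to 1:1 is not given, so I bracket it and ignore dropout:
- all 1:1: 232 / 2 = 116 health-IT patients;
- all 1:1:1: 232 × 2/3 = 154.7, about 155.

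The justification can be read with 20% and 9% as shares of all patients or as shares of readmissions. I show both.

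| Assumed health-IT readmission rate | n = 116 | n = 155 |
|---|---|---|
| No effect: 0.33 | 38 | 51 |
| Shares of all patients: 0.33 − (0.20 − 0.09) = 0.22 | 26 | 34 |
| Shares of readmissions: 0.33 − 0.33 × (0.20 − 0.09) = 0.2937 | 34 | 45 |

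The range is 26 to 51. It sizes the task and not the harm. The share of patients on lactulose or diuretics and the frequency of dose changes are not given, so the number of dose-related readmissions cannot be estimated.

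**The case against.** The strongest reply is that clinicians already oversee dosing. The protocol says that the app has no medical advice built in beyond when to call emergency services and is mainly a channel to the team, that staff use their training and not set responses, that decompensation is escalated, and that resulting care is standard of care. All of this stands, and it lowers the chance of harm. It does not supply a step that would recognise harm if it occurred.

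A second reply is that the SAE wording covers only SAEs simply associated with admissions, so an admission judged related could still be reported. That is fair: reporting is not forbidden. But nothing described produces such a judgement. Likewise, a dosing misunderstanding could be voted avoidable as a failure of communication. It would then count in the comparison, still without being identified as dose-related.

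A reader might go further and infer that the two lactulose rules are themselves a defect, because a patient who is both dehydrated and confused meets both and no priority is written. The documents do not support that. Such a patient is confused, which is a Table 3 contact trigger. So are fewer than 3 or more than 6 bowel movements a day on lactulose. Urgent matters go to the GI fellow on call and complex ones to the investigator or medical team. The training handouts and quick reference sheets given to dyads are not reproduced, so sequencing instructions may exist there. A one-line clarification would be welcome, but its absence is not a defect on its own.

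**Conclusion.** The gap is real and concerns safety reporting. Relatedness is presumed for readmissions as a class, on wording about the app itself, while the intervention includes dose changes, and no described review tests the presumption. It should be corrected. The conclusion rests on the text as supplied; an operating procedure outside these documents could already contain the check.

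A reader might also infer that dose-related admissions would be lost from both the safety record and the efficacy result and so distort the comparison. That is speculative. It requires a dose-related admission to be voted unavoidable, and the event would still count as a readmission. One such case lowers the health-IT avoidable rate by 100/155 = 0.65 to 100/116 = 0.86 percentage points. The planned difference is 20 − 9 = 11 points if the rates are shares of all patients, equal to 13 to 17 cases (116 × 0.11 = 12.8; 154.7 × 0.11 = 17.0). It is 0.33 × 11 = 3.6 points if they are shares of readmissions, equal to 4 to 6 cases (116 × 0.0363 = 4.2; 154.7 × 0.0363 = 5.6). Nothing in the documents suggests such numbers. A few cases would matter for safety and little for the estimate.

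**What to change.** Amend the SAEs paragraph. For each health-IT readmission, the site investigator, outside the blinded committee, uses the app dose log, the documented instructions and the discharge summary to record whether lactulose or a diuretic was changed under the programme since discharge, on whose instruction, and whether the change may have contributed. Possibly related admissions go to the IRB and are given as a count beside the avoidable readmissions. Because the records already exist, the form can also be completed for readmissions that have already occurred.

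The cost is one amended rule and one short form per health-IT readmission, about 26 to 51 in all, with no new visits or data sources. The judgement is unblinded and has no control-group counterpart, so the count is descriptive safety information and must not be used as a between-group comparison. The committee's material and blinding stay as they are.

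Optionally, add one line to the lactulose item saying that when dehydration and confusion occur together the dyad contacts the clinical team before changing the dose.
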